#### 6.7. Additional Analyses Depicting COVID-19 Pandemic Impact

- An anchor date will be used as a start date for COVID-19 pandemic related periods in analyses.
  - For China sites, the date COVID-19 was identified as the causative agent of outbreak in Wuhan by the China Center for Disease Control and Prevention (January 9, 2020) will be used as the anchor date for COVID-19 pandemic.
  - For non-china sites, the date the World Health Organization designated COVID-19 as a global pandemic (March 11, 2020) will be used as the anchor date.
- The date the World Health Organization declared COVID-19 over as a global health emergency (May 5, 2023) will be used as the end date for COVID-19 pandemic related periods in analyses.
- A summary table showing visits attended both before and after the anchor date will be produced. Visit attendance will be based on physician global evaluation of disease activity data.
- A separate summary table solely for subject discontinuations related to COVID-19 pandemic, if any, will be provided.
- Protocol deviations related to COVID-19 pandemic will be summarized and listed separately. Both important and non-important PDs related to COVID-19 pandemic will be reported.
- COVID-19 related AEs, if any, will be reported separately.

- A summary table showing AEs reported both before and after the anchor date will be produced. This summary will consider windows of equal duration before and after the anchor date.

## **7. INTERIM ANALYSES**

There are no planned formal interim analyses. Interim analyses may be performed for study monitoring for internal decision making, regulatory purposes or for planned publications.

The final analysis will be performed following the official database release.

This study is not randomized, and all treatments are open-labeled.

## 9. APPENDICES

### Appendix 1. Data Derivation Details

#### Appendix 1.1. The JIA Core Set Variables

The JIA ACR Response and Flare Criteria assessment (Giannini 1997) is a derived measurement of the 6 components of the JIA core set variables, which includes:

- Physician global evaluation of disease activity.
- Number of joints with active arthritis.
- Number of joints with limited range of motion.
- Parent/legal guardian/subject evaluation of overall well-being (from the CHAQ).
- Functional ability (Disability Index from the CHAQ).
- ESR.

The ACR definition of active arthritis is any joint with swelling, or in the absence of swelling, limitation of motion accompanied by either pain on motion or tenderness not due to deformity.

#### Appendix 1.2. The JIA Joint Counts

For swollen joints, painful/tender joints and joints with limitation of motion, respectively, before calculating the joint count, the following pre-processing step for each joint should be performed:

- If a joint receives an intra-articular injection (either at Baseline or post-baseline visits), set the joint status to “Present” on or after the date of injection.
- If the site of injection is not recorded and/or cannot be identified, the joint assessment on the CRF (either “Present” or missing) will be used.

After this pre-processing, a joint assessment that is missing is considered “absent”, thus a good joint. To calculate the number of joints with active arthritis and the number of joints with limited range of motion, only “present” joints will be taken into account.

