6. Intra-articular steroid (eg, triamcinolone (KENALOG[®], Aristospan[®])) should be administered to no more than four joints in any given 6 month period and individual joints should not be injected any more frequently than once in a 6-month period. Injected joints will be considered as not assessed during the remainder of the study. Intra-articular injections should be avoided during the 6 weeks prior to a study visit.

A UNIFORM TAPERING OF A MEDICATION OR TITRATING UP ON A DOSAGE OF MEDICATION TOWARD A SPECIFIC PRE-DETERMINED GOAL DOSAGE (INCLUDING DISCONTINUATION) WILL BE CONSIDERED A SINGLE CHANGE IF ACCOMPLISHED WITHIN 1 MONTH.

Appendix 4. Permitted Adjustments (Tapering) of JIA Medications for Subjects with Inactive Disease for at Least 24 Weeks

Subjects who have inactive disease for at least 24 consecutive weeks may begin to taper off of concomitant JIA therapies and tofacitinib. Tapering of therapies is to be completed in the following order: oral corticosteroids, MTX/leflunomide, tofacitinib.

- For subjects who are not taking concomitant oral corticosteroids, tapering will start with MTX/leflunomide, followed by tofacitinib.
- For subjects who are not taking concomitant MTX/leflunomide, tapering will start with oral corticosteroids, followed by tofacitinib.
- For subjects not taking concomitant oral corticosteroids or MTX/leflunomide, tapering will start with tofacitinib.

The rate at which each drug is tapered is described below.

Oral Corticosteroids: The dose of oral corticosteroids may be reduced or discontinued for subjects who have inactive disease for at least 24 consecutive weeks (time in parent study and A3921145 inclusive). The dose can be reduced by 0.1mg/kg each week. Once the dose of corticosteroids is at 5 mg/day then an absolute decrease by 1 mg/day each week can be implemented.

Methotrexate/leflunomide: The dose of MTX/leflunomide may be decreased or discontinued for subjects who continue to have inactive disease for at least 24 consecutive weeks after receiving the last dose of oral corticosteroids. MTX/leflunomide may be discontinued with or without tapering based on local practice; it is acceptable to stop the drug abruptly or by tapering the dose.

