Intravenous or intramuscular corticosteroids, biologic response modifiers and DMARDs other than those specified as allowed DMARDs ([Appendix 1](#)) are not allowed during this study. Intra-articular corticosteroids (eg, triamcinolone (KENALOG[®], Aristospan[®])) may be given in no more than four joints in a six month period. Injections should be avoided for 6 weeks before any study visit. Injected joints will also be considered as not assessed for the remainder of the trial

Acetaminophen/paracetamol is not permitted as a part of combination products such as over-the-counter “cold remedies” or in combination with opioids if the acetaminophen/paracetamol dose will exceed 2.6 gm/day. Subjects who require rescue for more than 10 consecutive days should be considered for allowed JIA medication adjustments or discontinued from the trial. In addition, subjects should not be dosed with rescue acetaminophen/paracetamol or opioids during the 24 hours prior to a study visit. Baseline stable acetaminophen/paracetamol or opioids should NOT be discontinued in advance of study visits.

Subjects should not be dosed with any rescue intervention within 24 hours prior to a study visit unless indicated for subject safety and individual case management at the discretion of the investigator.

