Appendix 14. Alternative Measures During Public Emergencies

The alternative study measures described in this section are to be followed during public emergencies, including the COVID-19 pandemic. This appendix applies for the duration of the COVID-19 pandemic globally and will become effective for other public emergencies only upon written notification from Pfizer.

Use of these alternative study measures are expected to cease upon the return of business as usual circumstances (including the lifting of any quarantines and travel bans/advisories).

1. Eligibility

Subjects from the A3921165 study will be able to enter this study if eligible (See [Section 4 SUBJECT SELECTION](#)).

While SARSCoV2 testing is not mandated for this study, local clinical practice standards for testing should be followed. A patient should be excluded if he/she has a positive test result for SARS-CoV2 infection, is known to have asymptomatic infection, or is suspected of having SARS-CoV2. Patients with active infections are excluded from study participation as per [Section 4.2 Exclusion Criteria](#).

2. Telehealth Visits

In the event that in-clinic study visits cannot be conducted, every effort should be made to follow up on the safety of study participants at scheduled visits per the Schedule of Activities or unscheduled visits.

Telehealth visits may be used to continue to assess participant safety and collect data points. Telehealth includes the exchange of healthcare information and services via telecommunication technologies (eg, audio, video, video-conferencing software) remotely, allowing the participant and the investigator to communicate on aspects of clinical care, including reminders, education, and safety monitoring.

Follow the protocol [schedule of activities](#) when possible, except for the patient reported outcomes which cannot be completed over the phone. The following assessments must be performed during a telehealth visit :

- Review and record study intervention(s), including compliance and missed doses.
- Review and record any AEs and SAEs since the last contact. (See [Section 8 ADVERSE EVENT REPORTING](#)).
- Review and record any new concomitant medications or changes in concomitant medications since the last contact.

- Review and record contraceptive method and results of pregnancy testing. Confirm that the participant is adhering to the contraception method(s) required in the protocol. See [Section 4.3.1 Contraception](#).

3. Home Health Visits

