### **Appendix 1.6. Juvenile Arthritis Disease Activity (JADAS-27 CRP and JADAS-27 ESR) Score**

JADAS-27 CRP and JADAS-27 ESR score consists of four components (Consolaro 2009, Bazso 2009, Nordal 2012):

- Physician global assessment of disease activity;
- Parent/legal guardian/subject global assessment of Child well-being (from the CHAQ);
- Number of joints with active disease (27 joint assessment);
- CRP or ESR.

The 27 joints used here are bilateral Elbow, Wrist, MCP 1-3, PIP 1-5, Hip, Knee and Ankle, plus Cervical Spine.

The CRP value will be normalized to a 0 – 10 scale according to the following formula:

$$(\text{CRP (mg/L)} - 2.87)/10$$

Before calculation, CRP values <2.87 mg/L will be converted to 2.87 and CRP values >102.87 mg/L will be converted to 102.87. The value 2.87 (mg/L) here is the upper bound of the reference range provided by the lab.

The ESR value will be normalized to 0 – 10 scale as below:

$$(\text{ESR} - 20)/10$$

Before calculation, ESR values <20 mm/h will be converted to 20 and ESR values >120 mm/h will be converted to 120.

JADAS-27 CRP/ESR score will be calculated as the simple linear sum of the scores of its 4 components, which yields a global score of 0 – 57 for the JADAS-27 CRP/ESR score.

If any of the components is missing, the JADAS-27 CRP/ESR score will be considered missing.

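### SAP Appendix 1.2 counts a missing joint assessment as a healthy joint without requiring that the joints were examined, and its rule for injected joints is not reconciled with the protocol

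*SAP*

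**What the plan says.** **Missing joints.** SAP Section 5.3 declares missing joint assessments an exception to the no-imputation rule and points to Appendix 1.2, which says: "After this pre-processing, a joint assessment that is missing is considered" absent, and the joint therefore good. No minimum number of assessed joints is given, and nothing requires that an examination was done at the visit.

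**Injected joints.** The same appendix handles these first, for swelling, pain/tenderness and limitation of motion alike: "If a joint receives an intra-articular injection (either at Baseline or post-baseline visits), set the joint status to" Present from the injection date, with no end date. If the injection site is unknown, the CRF value is used.

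**The protocol on injected joints.** Appendix 3, item 6: "Injected joints will be considered as not assessed during the remainder of the study". Appendix 7: "Injected joints will also be considered as not assessed for the remainder of the trial".

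**Visits without a joint examination.** Protocol Appendix 14 foresees remote contact: "Telehealth visits may be used to continue to assess participant safety and collect data points". Its list of what must be done at such a visit covers dosing, adverse events, concomitant medication and contraception, but not joints.

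**Other missing-data rules.** JIA ACR response is missing if the available components cannot settle it (SAP Appendix 1.3), and flare follows the same rule (1.4). Clinical inactive disease needs every component present (1.5). For JADAS-27: "If any of the components is missing, the JADAS-27 CRP/ESR score will be considered missing" (1.6).

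**The concern.** The other rules in SAP Appendix 1 stop a composite endpoint from being declared on data that were not collected. A joint count that can never be missing does not trigger them. Followed as written, the plan cannot tell a child with no active joints from a child whose joints nobody examined, and it scores the second as the first. The secondary objective is persistence of efficacy, and change in both joint counts is a named endpoint.

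The injection rule works the other way. It fixes a joint as affected for the rest of follow-up, whatever its later state, and the SAP does not explain how this follows from the protocol's not-assessed status.

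**Working it through.** No stated figure in the plan rests on these rules, so there is none to reproduce. The cutoffs below come from SAP Appendices 1.3 to 1.7; the joint counts are illustrative assumptions. Percent change = 100 × (follow-up − reference) / reference.

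**1. Examination missed after baseline.** Assume reference counts of 10 active and 6 limited joints and no true change.
- Active: (0 − 10)/10 = −100%. Limited: (0 − 6)/6 = −100%. The true change is 0% in both.
- The change endpoints read −10 and −6.
- A reference count of 0 gives 0% and does no harm.

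**2. Flare.** Flare needs at least 3 of 6 variables worse by 30% and no more than 1 better by 30%. If both Month 3 counts are at least 1, a missed later examination makes two variables improve by 100%. Since 2 > 1, core-set flare is ruled out on the joint counts alone. The fever route for sJIA stays open.

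**3. Examination missed at Month 3.** Both flare reference counts become 0. If the zero-baseline rule of Appendix 1.3 also applies to flare (1.4 refers to 1.3 only for missing components), any later count above 0 is a 999999% worsening. The two-joint minimum still applies, so a later count of 1 does not qualify and a count of 2 or more does. A true fall from 10 to 4 (−60%) would be scored as worsening.

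**4. CHAQ and ESR collected, joints not examined.**
- ACR: with both baseline counts above 0, two of the three improved variables needed are supplied at every threshold from 30 to 100. One of the other four completes the response if no more than one worsens.
- Clinical inactive disease: the no-active-joints condition is met by imputation.
- JADAS-27: the joint component becomes 0, so the score is too low by the true number of active joints among the 27.

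**5. Purely remote visit.** Parent-reported outcomes cannot be completed by phone (Protocol Appendix 14). A CHAQ taken by phone is invalid and removes the visit from ACR, flare and JADAS summaries (SAP 6.2). ESR and CRP are not on Appendix 14's local-laboratory list. At most the physician global and two imputed counts remain.
- ACR: three unknown variables could have worsened and only one may, so a response cannot be established.
- JADAS-27: missing, because the parent global is missing.
- Clinical inactive disease: cannot be declared without ESR or CRP.
- Still exposed: the two joint-count summaries, and flare scored as not occurring when CHAQ was simply not collected.

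**6. Single blank joints.** Baseline 10, true follow-up 8: −20%. With one active joint blank, 7 are counted: −30%, and the ACR30 component is gained. At baseline the effect reverses: 10 true joints with 2 blank count as 8, and a follow-up of 7 reads (7 − 8)/8 = −12.5% instead of −30%.

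**7. Injected joints.** Setting all three findings to Present makes a joint active if swelling is assessed there, or limitation together with pain. In Protocol Section 7.1.3 only the sacroiliac joints have neither swelling nor limitation assessed. For any other joint, one injection bars clinical inactive disease, and so remission, at every later visit. If the rule carries into JADAS-27, k injected joints among the 27 make the score at least k:

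| k | Inactive (≤1) | Minimal activity (≤2.0) | Minimal activity (≤3.8) |
|---|---|---|---|
| 1 | possible | possible | possible |
| 2 | no | possible | possible |
| 3 | no | no | possible |
| 4 | no | no | no |

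For flare, two injected joints that were neither active nor limited at Month 3 add 2 to each count, if limitation is assessed there. This meets the 30% rule at a reference count of 6 (2/6 = 33.3%) but not 7 (2/7 = 28.6%).

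**The case against.** **A blank joint may mean normal.** Appendix 1.2 describes the CRF value as Present or missing, which suggests that only findings are ticked. For an examined child, blank = absent then simply decodes the form. That stands, and it is why an examination-level condition is needed: the documents do not separate this blank from an unexamined joint. A programmer might apply the rule only where a joint form exists, but the SAP does not say so.

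**Remote visits are mostly protected.** A reader might infer that telehealth visits produce false ACR responders or false inactive disease. Step 5 shows that they mostly cannot.

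**Present can be a conservative imputation.** A reader might infer that the two documents give the same joint opposite scores. They do not: the protocol gives a data status and no score, and the SAP may modify the protocol. Without the Present rule, the missing-joint rule would count an injected joint as healthy. Nor does the protocol prescribe excluding injected joints and prorating the count; neither document mentions it. As the main analysis, that would stop a steroid-injected joint counting against inactive disease in an open-label single-arm study, so it is a trade-off.

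What remains is the lack of an end date and of any stated rationale. If the site is unknown and the CRF is blank, the injected joint ends up absent. Appendices 1.3 and 1.4 flag their departures from an index protocol; 1.2 flags none.

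**Two injections are not a flare.** They supply at most two of the three worsened variables. If the joints were already active and limited at Month 3, they add nothing.

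**Conclusion.** The missing-joint rule, followed literally, gives a wrong result when no joint examination was done: complete resolution in both joint-count endpoints and, with both Month 3 counts non-zero, no core-set flare. A missed Month 3 examination corrupts the flare reference in the other direction. ACR response, clinical inactive disease and JADAS-27 are at risk mainly at visits with CHAQ and ESR but no joint examination. This assumes that the rule is programmed as written.

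The injected-joint rule is defensible as an imputation, but it is unexplained, has no end date and is not tied to the protocol text.

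A reader might conclude that all joint-based endpoints are mis-scored. The documents do not support that: only subject-visits with an unexamined or injected joint are touched, their frequency is not given, and a changed joint count need not change a composite. The primary safety endpoints and the tapering endpoints do not use joint counts. The affected endpoints are secondary and descriptive, so no error rate or sample size is involved.

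**What to change.** 1. In SAP Appendix 1.2, apply missing = absent only when the joint examination is recorded as done at that visit, including baseline and Month 3. Otherwise set both joint counts to missing and let the existing component rules decide. State what a blank joint on the CRF means.
2. Reconcile SAP Appendix 1.2 with Protocol Appendices 3 and 7 on injected joints. If Present is a deliberate conservative imputation of the not-assessed status, say so, and say that it has no end date.
3. Add a sensitivity analysis that leaves injected joints out of both reference and follow-up counts. The only supportive analyses now planned (SAP 6.2.1) concern ESR kits.

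The cost is a few lines of SAP text, one examination-done flag, one extra set of descriptive tables and slightly more missing joint counts.

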#### Appendix 1.3. JIA American College of Rheumatology (ACR) Response

The assessments using JIA ACR 30, 50, 70, 90 and 100 will be performed. Other responder criteria may be assessed if appropriate. The JIA ACR 30, 50, 70, 90, 100 response criteria (Giannini 1997) are as follows: 3 out of 6 JIA core set variables improved  $\geq 30\%$ , 50%, 70%, 90%, 100%, respectively, with no more than 1 out of 6 JIA core set variables worsened by  $\geq 30\%$ . Only ESR will be used to calculate ACR responses.

If the value in any of the components at a timepoint is missing, the component variables that are not missing will be used to determine the response status. As a general principle, if there are sufficient non-missing components to determine whether the JIA ACR endpoint is a response or non-response, then JIA ACR endpoint is not missing, else if the available non-missing components are not sufficient to determine the response status of JIA ACR endpoint then it is considered missing.

In order to avoid numerical difficulty, if the baseline value of any component is equal to 0, the following algorithm will be used in evaluating the percent change from baseline:

1. If change from baseline is also equal to 0, then percent change from baseline is set to be 0%;
2. If change from baseline is  $> 0$ , then percent change from baseline is set to be 999999%.

These percentages will be used to derive the JIA ACR endpoints. Change from baseline cannot be  $< 0$  since none of the components should have negative value.

In subjects with systemic JIA, absence of fever due to sJIA in the preceding 7 days is also required (Ruperto 2012). Note that here is different from index study A3921104 protocol, where only absence of fever due to sJIA is required (no requirement of timeframe).

#### Appendix 1.4. Disease Flare

JIA ACR flare (Brunner 2002) is defined as a worsening of 30% or more in 3 or more of the 6 variables of the JIA core set listed above, with no more than one variable improving by 30% or more. In addition, the following minimum worsening contingencies apply: if either the number of active joints or the number of joints with limited range of motion is included in the calculation of "flare" then there must be a worsening of at least two joints. If the Physician's or parent/legal guardian global rating scores are used in the definition of "flare" then there must be a worsening of at least 2 units on the 10-unit scales. If the ESR is used in the definition of "flare" then the second value for the ESR used in the calculation must be above the upper limit of normal for the ESR.

In addition, for subjects with sJIA from A3921104 and A3921165, a disease flare may also constitute a recurrence of fever due to sJIA of  $>38^{\circ}\text{C}/100.4^{\circ}\text{F}$  (oral) or  $>101.4^{\circ}\text{F}/38.6^{\circ}\text{C}$  (rectal) on 2 or more consecutive days (Ruperto 2012). Note that here is different from index study A3921104 protocol, where 2 or more consecutive days for fever was not required.

Missing component handling will be the same as that for JIA ACR responses (See [Appendix 1.3](#)).

## **Appendix 1.5. JIA ACR Clinical Inactive Disease Status Determination and Clinical Remission Criteria**

The American College of Rheumatology (ACR) JIA Clinical Inactive Disease and Clinical Remission (Wallace 2011) criteria is defined as follows:

### **The Clinical Inactive Disease:**

The Clinical Inactive Disease Status Determination assessment is a derived measurement and defined as follows: which includes:

- No joints with active arthritis.
- No fever, rash, serositis, splenomegaly, hepatomegaly, or generalized lymphadenopathy attributable to JIA.
- No active uveitis (as defined by the SUN Working Group).
- ESR or CRP levels within normal limits in the laboratory where tested or, if elevated, not attributable to JIA. There will be two endpoints: Clinical Inactive Disease Status defined by ESR and Clinical Inactive Disease Status defined by CRP.
- Physician global evaluation of disease activity score of ‘best possible’ on the scale used.
- Duration of morning stiffness of  $\leq 15$  minutes.

Since uveitis exam will be performed annually, for the purpose of determining JIA ACR Inactive Disease status, the last uveitis assessment result will be carried forward up to the next non-missing uveitis assessment prior to study discontinuation.

After the pre-processing of uveitis assessment, if any of the components is missing, the components that are not missing will be used to determine the Clinical Inactive Disease Status as follows:

- Inactive disease: all components must be present (non-missing) and meet all conditions.
- Active disease: at least one component is present (non-missing) and does not meet the condition.
- Not determined: any other scenarios.

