Risk Factor Check for Venous Thromboembolism ¹⁶	X ^d	X ^d	X ^d	X ^d	X	X	X	X	X
Prior/Concomitant Medications	X	X		X	X	X	X	X	X
Childhood Health Assessment Questionnaire (CHAQ)		X			X	X	X	X	X
Vital signs: Blood pressure (BP), Pulse Rate (PR), Temperature ¹	X	X		X	X	X	X	X	X
Complete Physical Exam ^{15, 17}	X				X ^a	X ^a		X ^a	X ^a
Targeted Physical Exam ^{2, 17}		X		X	X	X	X		

Protocol Activity	Subjects >14 days after EOS ⁷ Visit		Combined with EOS ⁷ Visit	Separate Visit within 14 days after EOS ⁷ Visit	Year 1 Months 1, 3, 6, 9, 12 ⁸	Years 2-5 Every 3 Months ⁸	Years 6-10 Every 3 months (except at Months 72, 84, 96, 108, 120) ⁸	Years 6-10 Months 72, 84, 96, 108, 120 ⁸	End of Study /Early Termination
	Screening	Baseline	Screening /Baseline	Screening /Baseline					
Tanner Stage Assessment		X ^b			(annually) ^b	(annually) ^b		(annually) ^b	X ^b
Physician Global Evaluation of Disease Activity	X	X		X	X	X	X	X	X
Joint Assessment of Active Arthritis (Swelling, Pain/Tenderness) and Limitation of Motion	X	X		X	X	X	X	X	X
Duration of Morning Stiffness Assessment	X	X		X	X	X	X	X	X
Signs and symptoms of Systemic Disease (sJIA ONLY)	X	X		X	X	X	X	X	X
Assessment of JIA-associated Fever (sJIA ONLY) ¹⁴	X	X		X	X	X	X	X	X
Tender Enthesal Assessment (ERA ONLY) ¹¹		X			X ¹¹	X ¹¹	X ¹¹	X	X
Modified Schober's Test (ERA ONLY) ¹¹		X			X ¹¹	X ¹¹	X ¹¹	X	X
Overall Back Pain and Nocturnal Back Pain Assessment (ERA ONLY) ¹¹		X			X ¹¹	X ¹¹	X ¹¹	X	X
PGA of Psoriasis (PsA ONLY) ¹²		X			X ¹²	X ¹²	X ¹²	X	X
BSA affected by psoriasis (PsA ONLY) ¹²		X			X ¹²	X ¹²	X ¹²	X	X
Investigator ACR30 Response Assessment (Applicable to Canadian Investigator Sites Only) ¹⁰					X ¹⁰	X ¹⁰	X ¹⁰	X ¹⁰	
QuantiFERON or Mantoux PPD/Chest Radiograph, if Applicable ³	X ³				(annually) ³	(annually) ³		(annually) ³	
Safety Laboratory Testing ⁴	X	X		X	X	X	X	X	X
Contraception check ^e	X ^e	X ^e	X ^e	X ^e	X ^e	X ^e	X ^e	X ^e	X ^e
Lipid Panel ⁵		X			X ⁵	X ⁵		X	X

Protocol Activity	Subjects >14 days after EOS ⁷ Visit		Combined with EOS ⁷ Visit	Separate Visit within 14 days after EOS ⁷ Visit	Year 1 Months 1, 3, 6, 9, 12 ⁸	Years 2-5 Every 3 Months ⁸	Years 6-10 Every 3 months (except at Months 72, 84, 96, 108, 120) ⁸	Years 6-10 Months 72, 84, 96, 108, 120 ⁸	End of Study /Early Termination
	Screening	Baseline	Screening /Baseline	Screening /Baseline					
Human Immunodeficiency Virus (HIV) Serology, Hepatitis B, Hepatitis C ⁹	X								
C-Reactive Protein (CRP)	X	X		X	X	X	X	X	X

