7.2.5. Uveitis Exam

Uveitis exam must be performed by an ophthalmologist (or qualified equivalent per local practice) and will be done at Screening if no documented history of uveitis exam within past 6 months is available) then annually thereafter, and at the End of Study/Early Termination Visit if required

If there is documented history of uveitis exam within the past 6 months, the next exam will be done one year from the date of the previous exam, then annually thereafter, and at the End of Study/Early Termination Visit if required.

A uveitis exam at the End of Study/Early Termination Visit is not required if an exam has been performed within the past 6 months of the EOS/ET visit.

The window for this particular examination is ± 30 days relative to the visits where uveitis exam is to be performed. At all other visits the investigator should assess if there are potential changes in uveitis status and refer for formal evaluation if deemed clinically necessary. For JIA subtypes that may require more frequent uveitis examination, investigators should manage this type of examination according to local standard of care.

For subjects with sJIA, this exam is not required but if available, documentation of previous uveitis assessment(s) by an ophthalmologist (or qualified equivalent per local practice) should be reviewed, the date of the prior examination recorded, and the presence/absence of active uveitis documented. For subject with sJIA, the investigator should assess at all visits if there are potential changes in uveitis status and refer for formal evaluation if deemed clinically necessary.

Uveitis exam should be performed according to standard of care and the results (ie, a report) recorded in the source document. Development of new uveitis or worsening of existing uveitis according to Standardization of Uveitis Nomenclature (SUN) criteria should be reported as adverse events in the CRF.

The activity of the anterior chamber (AC) inflammation will be evaluated according to the SUN criteria, where the activity of AC inflammation is graded from 0 to 4 (grade/cells in field: 0/<1, 0.5+/1–5, 1+/6–15, 2+/16–25, 3+/26–50, 4+/>50) (Jabs 2005).¹²

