### **Clinical Remission on Medications:**

- Inactive disease as defined above for 6 months (24 weeks) continuously while on medications.

Clinical inactive disease and clinical remission status will be based on the investigator’s assessment of the above components.

Note that when calculating clinical remission, only inactive disease in this study will be included in the 24 weeks count.

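### Clinical Inactive Disease needs every component non-missing, but systemic features are scheduled only in sJIA and the uveitis exam is optional there: as written the rule gives 0% in non-sJIA subjects and a downward bias of unknown size in sJIA

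*SAP*

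**What the plan says.** SAP Appendix 1.5 builds Clinical Inactive Disease from six components and classifies each visit in three ways. The favourable label has the strictest test: "Inactive disease: all components must be present (non-missing) and meet all conditions". The unfavourable label needs much less, since a single recorded failure is enough: "Active disease: at least one component is present (non-missing) and does not meet the condition". Every visit that fits neither label goes into a third class: "Not determined: any other scenarios". One of the six components, listed without any subtype exception, is "No fever, rash, serositis, splenomegaly, hepatomegaly, or generalized lymphadenopathy attributable to JIA".

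The protocol's Schedule of Activities collects the matching data under rows labelled "Signs and symptoms of Systemic Disease (sJIA ONLY" and, in a separate row for temperature-related findings, "Assessment of JIA-associated Fever (sJIA ONLY". The visit lists in Protocol Section 6 place the same items under an sJIA-only heading. On uveitis, Protocol 7.2.5 states "For subjects with sJIA, this exam is not required". It goes on to ask that any available earlier documentation be reviewed and the presence or absence of active uveitis recorded, and that the investigator consider uveitis status at all visits. Appendix 1.5 carries the last uveitis result forward.

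SAP Table 2 reports inactive disease and clinical remission in all five analysis sets: sJIA1, sJIA2, pJIA, ERA and PsA. SAP Section 5.3 bars imputation except for Tanner stage and joint assessments. For remission, "only inactive disease in this study will be included in the 24 weeks count".

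**The concern.** A missing component can block an inactive classification but can almost never block an active one. That matters when components are absent by schedule and not by accident. Outside sJIA the systemic-feature component is not scheduled at all. In sJIA the uveitis component is present only if someone has documented it. Visits with truly inactive disease then move to *not determined*, while visits with active disease keep their label.

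Inactive disease and remission are among the secondary endpoints for persistence of efficacy. A percentage that depends on which forms a subtype receives would understate persistence, and by different amounts in different analysis sets.

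**Working it through.** The plan states no expected rate for this endpoint, so there is no figure to reproduce. The check has four steps.

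**1. The rule with one component missing.** The other five components can each be met or failed, giving 2^5 = 32 patterns. Under Appendix 1.5, 31 contain at least one failure and are active. The one pattern with all five met is not determined. None is inactive.

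**2. Non-sJIA subjects.** The systemic-feature component is unscheduled, so its recorded share is 0. The inactive count is therefore 0, and the rate is 0% whether *not determined* visits stay in the denominator or are dropped. Remission requires 24 weeks of inactive disease, so it is also 0%.

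**3. sJIA subjects.** Let p be the true inactive proportion and u the share of visits with every component recorded. Assume that u does not depend on disease state and that every truly active visit has at least one recorded failing component.

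- *Not determined* dropped: p·u / (p·u + 1 − p)
- *Not determined* kept in the denominator: p·u

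Neither p nor u is in the documents; the values below are assumptions that show the range.

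| u | p = 30%, dropped | p = 30%, kept | p = 50%, dropped | p = 50%, kept |
|---|---|---|---|---|
| 0 | 0% | 0% | 0% | 0% |
| 0.25 | 9.7% | 7.5% | 20.0% | 12.5% |
| 0.5 | 17.6% | 15% | 33.3% | 25% |
| 0.75 | 24.3% | 22.5% | 42.9% | 37.5% |
| 0.9 | 27.8% | 27% | 47.4% | 45% |
| 1 | 30% | 30% | 50% | 50% |

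Example: 0.30 × 0.5 / (0.30 × 0.5 + 0.70) = 0.15 / 0.85 = 17.6%.

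If only visits with all applicable components present are counted, active visits are restricted in the same way as inactive ones: p·u / [p·u + (1 − p)·u] = p. The bias disappears under the same assumptions.

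**4. Timing of remission.** Subjects who roll over on the day of their index-study final visit have no joint, physician-global, morning-stiffness, CRP or ESR assessment in this study on Day 1, so counting starts at Month 1.

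- Protocol visit windows: latest Month 6 minus earliest Month 1 is (180 + 10) − (30 − 5) = 165 days, against 24 × 7 = 168 required.
- The shortest Month 1 to Month 9 span is (270 − 10) − (30 + 5) = 225 days, so Month 9 qualifies.
- SAP analysis windows (Appendix 1.12): Month 1 covers Days 2–60 and Month 6 covers Days 136–225, so the span can reach 225 − 2 = 223 days.

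**The case against.** The best defence is that the 0% follows only if an unscheduled item is coded as missing. Appendix 1.5 says that status rests on the investigator's assessment of the components. Every subtype has a temperature reading and an examination of skin, abdomen and lymph nodes. Protocol Appendix 4 ties tapering to inactive disease in all subtypes, so investigators must judge it anyway. A sensible programmer might well code the component as met.

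This does not rescue the text. The same appendix calls the status a derived measurement. The general examination neither names serositis nor asks for attribution to JIA, and the SAP does not map it to this endpoint. Where the SAP wants a missing item treated as absent, it says so, as for joints in Appendix 1.2.

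It is also fair to say that the asymmetry is not a fault in itself: one failed criterion settles active disease, while one unknown cannot settle inactive disease. The fault is applying that logic to components that were never scheduled, without stating a denominator.

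A reader might draw three stronger conclusions, which the documents do not support:

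- *The endpoint is 0% by design in every set.* In sJIA the exam is optional, not absent. One documented status carries forward, so the bias runs from none to complete.
- *The pJIA set lacks the systemic component entirely.* SAP Section 4.4 includes systemic JIA subjects without active systemic features in that set, and the component is scheduled for them.
- *Remission at Month 6 is impossible for same-day rollovers.* It is out of reach only when visits fall within the protocol windows; the SAP windows admit longer spans, and no per-protocol set removes late visits.

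**Conclusion.** The point holds in a limited form. As written, Appendix 1.5 yields 0% inactive disease and remission in ERA, PsA and the non-systemic part of pJIA. This rests on reading an uncollected component as missing, which is what the words say. In sJIA the rate is biased downwards by an amount the documents cannot fix, because the share with a recorded uveitis status is not given. The figures above assume that recording is unrelated to disease state.

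A secondary gap affects non-sJIA subjects who enter within 14 days. They have no uveitis exam scheduled at entry, and the next may be due a year after the previous one. Appendix 1.5 neither admits nor excludes index-study exams, so early visits could stay undetermined even after the systemic-feature gap is closed.

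Same-day rollovers seen within the protocol windows first qualify for remission at Month 9. That follows from the stated choice to count in-study inactive disease only, and it needs no more than a note.

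Severity is should-fix. The study is descriptive, the endpoint is secondary, and JADAS inactive disease, reported in all five sets, needs neither component.

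**What to change.** Amend SAP Appendix 1.5 as follows.

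1. In non-sJIA subtypes, treat systemic features as not applicable and met unless recorded as present, for example on physical examination or as an adverse event.
2. Name the uveitis source. Allow the last index-study exam and, in sJIA, the documented or investigator-recorded presence or absence of active uveitis. Do not count a wholly unrecorded status as met in the main analysis, since that would impute a favourable result; show it as a sensitivity analysis.
3. Compute the percentage among visits with all applicable components present, and report the number not determined by visit and analysis set.
4. Note that same-day rollovers seen within the protocol windows first qualify for remission at Month 9.

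Also list the uveitis carry-forward among the exceptions in SAP Section 5.3, where it is absent. The cost is SAP wording and derivation code, with no new data collection.
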